* PI: Principal Investigator, CoI1: Co-Investigator 1, CoI3: Co-Investigator 3, T1-7: Therapist 1-7, N1: Nurse 1, N2: Nurse 2, N3: Nurse 3, SC2: Study Coordinator2.

Table 1: Data Collection Schedule

(2) Intervention:

There are a total of 96 visits: 48 FES assisted intervention visits scheduled 1 hour, 3 times a week for 4 months, and 48 non-FES assisted exercise regimen visits scheduled 1 hour, 3 times a week for 4 months.

3. Blinding, including justification for blinding or not blinding the trial, if applicable.

The evaluator will be blinded to group assignment for the following assessment, but we cannot use true blinding due to the intervention's sensory component:

- c. Severity of gleno-humeral subluxation
- d. Spasticity measurement
- e. Capabilities of the Upper Extremity test
- f. Jebsen-Taylor Hand Function test
- g. Box and Blocks test
- h. Action Research Arm test
- i. Functional Reach test
- j. Range Of Motion of the upper extremity joints
- m. American Spinal Injury Association (ASIA) exam

4. Justification of why participants will not receive routine care or will have current therapy stopped.

All subjects will continue to consistently perform their usual (“baseline”) amount of physical activity throughout the study, including performance of lower extremities assisted FES ergometry, home exercise stretching program, cardiovascular conditioning, etc. “Baseline” activity is defined as amount of physical activity performed for at least 1 month prior to enrollment. Routine care will not be interrupted.

5. Justification for inclusion of a placebo or non-treatment group.

Both groups will receive some type of intervention: upper extremity passive ergometry or FES assisted upper extremity ergometry. This way, the effect of FES application will be extracted.

6. Definition of treatment failure or participant removal criteria.

Treatment failure constitutes of:

- Increased pain (more than 3 points increase on the NRS).
- Increased shoulder subluxation (more than 1 cm).
- Decreased range of motion (more than 15 deg).

Subjects will be removed from the study if they:

- Requires significant hospitalization (that would interfere with physiologic processes proposed to be studied through the protocol, i.e. e-stim) – at the discretion of PI.
- Become pregnant.

7. Description of what happens to participants receiving therapy when study ends or if a participant's participation in the study ends prematurely.

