- 1] allows the stimulation of our proposed list of upper extremity muscles (supraspinatus; infraspinatus; teres major and minor; anterior, middle, or posterior deltoid; biceps; and triceps), which is more than the standard set of muscles (bilateral biceps, triceps and supraspinatus).
- 2] allows to change the timing of the stimulation (On/Off) to produce a smooth cycling motion.

4. FDA approved use description:

The device FDA indication for use are:

1. Relaxation of muscle spasms
2. Prevention or retardation of disuse atrophy
3. Increasing local blood circulation
4. Maintaining or increasing range of motion

5. IDE Info:

Not applicable

c. Study Statistics

1. Primary outcome variable.

Independent Variables

FES or no FES

Dependent Variables: to be measured at 0, 4, 5, 9 and 12months

Severity of gleno-humeral subluxation, measured by X-ray (not measured at 5 months).

Spasticity of the pectoralis, biceps, triceps, and long finger flexor muscles, measured with the Modified Ashworth.

Functional movement of the shoulder, measured with the Capabilities of the Upper Extremity (CUE) test.

Hand function, measured with the Jebsen-Taylor Hand Function (JTHF) and Box and Blocks (BB) tests.

Upper limb function measured with the Action Research Arm test (ARA) test.

Range Of Motion of the upper extremity joints (of the shoulder, elbow, wrist, and fingers/thumbs), measured with goniometry.

Pain, measured with the Numerical Rating Scale (NRS).

Neurological function, measured with the American Spinal Injury Association (ASIA) exam.

2. Secondary outcome variables.

Not applicable

3. Statistical plan including sample size justification and interim data analysis.

Data Analysis: Data will be collected in accordance with each instrument's standardized instructions, with the evaluator being blinded to group assignment. To obtain consistency and facilitate interpretation of the data, we will use means and standard deviations (SDs) to describe normally as well as non-normally distributed variables. Appropriate post-hoc statistical analysis will be used to compare between group means and repeated measures. Baseline tests of homogeneity will be used *a priori*. If statistically significant differences are found after the subjects are randomized to the two groups, they will be corrected in the post-hoc analysis. Results will be considered significant at $P<0.05$.

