Power analysis: Because upper extremity, FES-assisted ergometry training is a new intervention, we based our power analysis on previously completed studies that looked at the effect of FES on muscle mass (50, 51) and cardio-vascular conditioning (52-56). A sample size of 24 will allow us to detect a mean difference between the pre- and post-measures. Some of our outcome measures (CUE, JTHF, BB tests) have been shown to respond to many types of rehabilitative interventions, and we believe they will be particularly responsive to the type of training used here. One of our goals is to use the data obtained in this study to determine the magnitude of the effect so we can design future trials. If the magnitude is very small, however, it is unlikely to be clinically relevant. We would then be more likely to propose intensifying the intervention (e.g., by lengthening the periods of cycling) than to suggest increasing sample size.

4. Early stopping rules.

* Subject medical status:

- Requires significant hospitalization (that would interfere with physiologic processes proposed to be studied through the protocol, i.e. e-stim) – at the discretion of PI.
- Increased pain (more than 3 points increase on the NRS).
- Increased shoulder subluxation (more than 1 cm).
- Decreased range of motion (more than 15 deg).

* Subject not compliant:

- Fails to follow directions.
- Become pregnant.

XII. LABELING & STORAGE OF DATA & SPECIMENS

All paper study documents are stored in locked cabinets at the Broadwaycampus of the KKI-ICSCI. Access to the locked cabinets is strictly limited to the study team members listed on this protocol. The documents with identifiers (such as the consent forms, phone screening forms, and the document that links the subject study # to the identity of the subject) are stored in a study binder in a separate locked cabinet from hard copy data collection forms.

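### Treatment failure is defined, and used to stop subjects, one subject at a time, but the analysis compares only means and never compares failures or stops by treatment

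*Combined protocol and SAP*

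**What the plan says.** All references are to the combined protocol and SAP.

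- **XI.a.6** opens a list with "Treatment failure constitutes of" and gives three per-subject criteria: pain up by more than 3 NRS points, subluxation up by more than 1 cm, range of motion down by more than 15 degrees. A separate list, headed "Subjects will be removed from the study if they", contains only significant hospitalisation and pregnancy.
- **XI.c.4** (Early stopping rules) repeats the three failure thresholds under subject medical status, beside hospitalisation.
- **XI.c.1** lists pain, subluxation and range of motion among the primary dependent variables, as measured values. Failure, stopping and withdrawal are not listed. **XI.c.2** (secondary outcomes) is marked not applicable.
- **XI.c.3** describes the data by summary statistics: "we will use means and standard deviations (SDs) to describe normally as well as non-normally distributed variables". For comparison it says "Appropriate post-hoc statistical analysis will be used to compare between group means and repeated measures". It names no test, no analysis set and no rule for missing values.
- **XVII** and **XXI.d** provide for Medical Monitor review of serious or unanticipated events and for adverse event reports to the IRB. Both work event by event.

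**The concern.** The protocol treats a threshold crossing as the unit of harm for an individual, then analyses only averages of the same variables. Two things follow.

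First, a few clear failures can be offset by modest gains in everyone else, and the comparison of means then shows little.

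Second, the stopping rule may decide who stays in the data. Subluxation and range of motion are scheduled only at assessment visits, so a crossing on them in the first block would normally be found at month 4. If that subject then leaves assessment, there is no second-block value and no within-subject pair. A subject who fails in the second block is found at month 9 and has both values. Losses are thus one-sided: failures on FES drop out of a complete-pair contrast only when FES came first, and the contrast moves toward FES. The same holds in reverse for exercise.

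At stake is whether a reader of the final report can see how many subjects worsened on each treatment.

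**Working it through.** **Plan's own figures.** There is none for failures. The sample size of 24 is stated without effect size, SD, power or sidedness, so it cannot be reproduced. Every size below is assumed; only the thresholds, the 24 subjects, the 12:12 split and the visit schedule come from the documents.

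**1. Dilution, subluxation.** Four of 24 worsen 1.5 cm on FES and 20 improve 0.3 cm.
- Mean change = (4 × 1.5 − 20 × 0.3)/24 = 0.00 cm; failures 4/24 = 16.7%.
- SD of change, with a within-group SD of 0.3: sum of squares 4 × 1.5² + 20 × 0.3² = 10.8; √(10.8/23 + 0.09) = 0.75 cm, against 0.30 cm where nobody truly changes.

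**2. Dilution, pain.** In 12 FES subjects, three change by +4, six by −1 and three by −2: mean (12 − 6 − 6)/12 = 0.0, SD 2.45. Against 12 controls with mean 0.0 and SD 0.74, the t-test gives P = 1.00. The failure count is 3/12 = 25% (exact 95% CI 5.5% to 57.2%) against 0/12 (upper limit 26.5%).

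**3. Loss of pairs.** Four FES failures among 24, with half of all subjects FES-first, gives on average two failures without a second block, leaving 22 pairs. Mean of FES minus exercise, where positive is worse on FES and nobody changes on exercise:

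| Other 20 on FES | All 24 | After losing two |
|---|---|---|
| unchanged | 6/24 = 0.250 | 3/22 = 0.136 |
| improve 0.15 | (6 − 3)/24 = 0.125 | (3 − 3)/22 = 0.000 |
| improve 0.3 | (6 − 6)/24 = 0.000 | (3 − 6)/22 = −0.136 |

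The shift toward FES is 0.114, 0.125 and 0.136 cm.

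**4. Dependence on the test.** Take the last row, where the true mean difference is zero (SD 0.3 per change, 20,000 simulated trials). The share of trials significant in favour of FES was:
- complete-pair t-test: about 13% to 14%, where 2.5% is nominal;
- month-4 Welch comparison between groups: 3.6%;
- a repeated-measures model keeping incomplete subjects: 0.01% with clustered standard errors, 3.4% with a random-intercept model (under 400 runs).

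The false favour is therefore mainly a complete-pair effect.

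**5. Where means suffice.** With nobody stopped, 20 completers and a paired test, if the other subjects also do 0.15 to 0.3 cm worse on FES, the comparison of means detects it in 85% to 99% of runs.

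**6. What a table would show.** For example, 4/24 after FES (exact 95% CI 4.7% to 37.4%) and 0/22 after exercise (upper limit 15.4%). Fisher's test, treating these as independent, gives P = 0.11. With 12 per group it needs 5 against 0 (P = 0.037). The table can only describe.

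**7. Range-of-motion error.** XI.a.6 names no joint. Assume measurement error of change with SD 7 degrees and independent errors. P(apparent loss > 15) = P(Z > 15/7) = 0.0161 per joint-side. Over eight joint-sides, 1 − (1 − 0.0161)⁸ = 12.2%, or 2.9 false failures in 24 subjects. One shoulder movement on two sides gives 3.2%, or 0.8 in 24. For SD 5 to 10 the ranges are 0.3 to 10.2 and 0.06 to 3.1 subjects. Counting every joint could swamp the table.

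**The case against.** Most of the raw material is already there. The three failure components are primary dependent variables, measured per subject on schedule, so the count can be derived later. In a 24-subject trial with sessions supervised by the principal investigator, several stops would not go unnoticed. The planned SDs would often flag a split: in the simulated scenarios the ratio of the two SDs of change exceeded 1.6 in at least 96% of trials. All of this stands and lowers the weight of the point. It does not remove it. An SD gives neither direction nor count and helps only if SDs of change are shown. A count made after the results are known leaves the baseline, the joint and the denominator open to choice.

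Three stronger readings are tempting, and the documents do not support them.

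- *A masked mean would lead the investigators to raise the dose.* XI.c.3 does say of a very small effect, "We would then be more likely to propose intensifying the intervention (e.g., by lengthening the periods of cycling) than to suggest increasing sample size". That remark follows a sentence on the CUE, JTHF and Box and Blocks tests and concerns future trials. Nothing ties it to pain, subluxation or range of motion.
- *The analysis is biased toward FES.* That needs stopped subjects to leave assessment and a complete-pair test to be used. XI.c.4 does not settle the first, and XI.a.6 does not list threshold crossing as a reason for removal. XI.c.3 does not name the test.
- *FES is known to cause these failures.* XIII.a.2 lists pain at the stimulation site and a minimal risk of skin burn. Subluxation and loss of motion are possible harms, not listed ones.

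**Conclusion.** The point holds as a minor one. The plan defines failure per subject and stops subjects on it, yet plans no comparison of failures or stops by treatment. Harm in a minority can be diluted in a mean, with the planned SDs as a partial warning only. If assessments end with treatment, a complete-pair contrast is biased toward the treatment that caused the stop. In the worked example that bias is 0.11 to 0.14 cm, with false favour in about 13% to 14% of trials when the true mean difference is zero. These figures rest on assumed failure numbers, effect sizes and SDs; the documents allow no estimate of the real size. If the remaining subjects also do worse on FES, the means would usually show it. The mean comparisons themselves are not at fault.

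**What to change.** 1. **XI.c.4:** state that crossing a threshold stops the treatment, that scheduled assessments continue where the subject agrees, and that those data stay in the analysis.
2. **XI.c.2 or XI.c.3:** add one descriptive safety table of treatment failures (XI.a.6) and medical-status stops (XI.c.4), by component and by FES or non-FES block, with exact 95% intervals.
   - Denominator: every subject who started the block.
   - Baseline: the block's own start for pain and range of motion (months 0 to 4 and 5 to 9). For subluxation, the last prior X-ray (months 0 to 4 and 4 to 9), labelled as such because there is no month-5 film.
   - Range of motion: one shoulder movement named in advance.

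The cost is a few lines and one table from measurements already scheduled, plus the remaining assessment visits of any stopped subject. The limits should be stated with the table: intervals are wide, so no formal test; pain is rated unblinded (Table 1); and range-of-motion counts still contain measurement error.

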XVII. ADVERSE EVENTS.....	28

XVIII. CHANGES TO PROTOCOL	28
a. Protocol Modifications:	28
b. Protocol Deviations:	28
XIX. CONTINUING REVIEW & FINAL REPORT	28
a. Continuing Review Reports:.....	28
c. Final Study Report:.....	29
XX. LITERATURE REVIEW	29
XXI. Appendix: Study Related Documents.....	32
a. Recruitment forms:.....	32
b. Informed Consent forms:.....	32
c. Case Report Forms:	32
d. Serious Adverse Event report forms:.....	32
XXII. Appendix: Medical Device Related Documents.....	33

VI. STUDY INFORMATION**a. Type of Research**

This is Specific Aim 1 of Proposal 08284002 titled "Advanced Restoration Therapies in Spinal Cord Injury".

Specific Aim 1: To determine whether functional electrical stimulation promotes neurological and physical recovery in patients with Spinal Cord Injury.

We will investigate the extent of functional recovery in patients with Spinal Cord Injury (SCI) who receive Functional Electrical Stimulation (FES) in the upper extremities compared with patients who do not receive FES.

b. Abstract

Background: Recent evidence suggests that FES can improve certain functions in the Central Nervous System (CNS) following injury or disease; it can enhance motor recovery, change H reflex and flexor reflex excitability [1-3] and enhance sensory function in chronic SCI [4].

Using FES-based therapies in our clinic, we have seen neurological, physical, and functional improvements. By systematically measuring the impact of FES on functional recovery in individuals with spinal cord related paralysis, we hope to greatly advance our clinical application of FES.

Objective/Hypothesis: To test the hypothesis that patterned neural activity induced by FES enhances recovery of function in the injured spinal cord patients with paralysis.

Study Design SA1: A randomized, controlled, single-blinded, in-subject controlled (A-B type) trial will be performed in patients with SCI receiving an upper extremities non-FES assisted exercise protocol compared with patients receiving upper extremities ergometry in combination with FES. Neurological and functional outcome measures will be obtained at baseline (time 0), after 1st 4 months of intervention (4 months), after 1 month washout (5 months), after 2nd 4 months intervention (9 months), and 3 month after completing the last intervention (12 months).

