Military Significance: Traumatic injury to the Central Nervous System (CNS) is an increasing problem for the U.S. military, given the increasing number of soldiers with SCI returning from combat zones. Our proposed project will address this specific need by developing rehabilitative programs and training tools as well as advanced technologies for restoring nerve cell function. Understanding the underlying mechanisms that promote regeneration and recovery, as outlined in this proposal, will contribute to the knowledge base in the field as well as advance current concepts of regeneration. Overall, the aims of this proposal have direct and indirect relevance to military and related civilian populations.

Public Purpose: SCI is a devastating condition that imposes major costs on individuals and society. Close to 12,000 traumatic injuries occur each year in the United States, and approximately 1 million people live with SCI. Moreover, military personnel have returned from combat zones with SCI in the past years. Estimates for lifetime financial burden per individual range from \$500,000 to \$2 million, and costs for SCI patient care in the United States exceed \$7 billion dollars. Including non-traumatic spinal-cord lesions, such as those associated with multiple sclerosis, would quadruple the number and annual cost of U.S. SCI cases [43]. However, virtually all current treatments must be applied shortly after the onset of SCI, as there are not yet effective treatments for the chronic phase of injury [4]. Effective treatment and therapeutic strategies geared toward the chronic injury phase would both improve the lifestyles of people with SCI and decrease their financial burden.

b. Study Design, Research Objectives

Study Design: A 12 months randomized, controlled, single-blinded, in-subject controlled (A-B type) trial will be performed in patients with SCI receiving upper extremity ergometry in combination with FES versus an upper extremities non-FES assisted exercise protocol. Neurological and functional outcome measures will be used at 0, 4, 5, 9, and 12 months to test the efficacy of each intervention.

Specific Aim: Does FES of the upper extremities promote neurological and functional recovery?

Hypothesis 1: Patterned FES of arm and shoulder muscles, via upper extremity ergometry, will improve physical and neurological function in individuals with paralysis resulting from spinal cord injury.

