n) Pain and Spasticity Medication inventory: This is a routine exam performed for people with spinal cord injury. Pain and antispasticity medications dose will recorded.

o) FES Evaluation: This is a routine exam performed for people with spinal cord injury prior to receiving FES. Therapist 1 or 6 will test the different muscles that are targeted for this study to achieve the best motor response to FES, and maintain subject comfort. Depending on the neurological level of the subject, the muscles are: supraspinatus; infraspinatus; teres major and minor; anterior, middle, or posterior deltoid; biceps; and triceps.

(2) Intervention:

The subjects will be randomly assigned, in a one-to-one ratio, either to group 1, which will first engage in the FES assisted ergometry followed by the non-FES assisted exercise, or to group 2, which will first engage in the non-FES assisted exercise followed by the FES assisted ergometry.

p) FES Upper Extremity Cycle Ergometry: While undergoing the FES assisted ergometry intervention, the subjects will use an RT300-SLSA upper extremity ergometer configured with FES. Electrode placement will be individually optimized to produce smooth cycling, as measured by crank symmetry, average stimulation level, expended energy per hour, and muscle stiffness. Parameters of stimulation current will also be individually optimized to achieve the best motor response (frequency of 10 to 100 Hz, pulse duration of 50 to 500 μ s, and amplitude of 10 to 140 mA). Silver mesh self-adhesive surface electrodes will be used to conduct the stimulation. They will activate some combination of the following muscles, depending on the neurological level at which they are applied: supraspinatus; infraspinatus; teres major and minor; anterior, middle, or

posterior deltoid; biceps; and triceps. Target cycling speed will be 20 rpm, with a resistance of 0.965Nm. The subjects will warm up between 2 and 10 minutes depending on muscle stiffness or spasms, actively cycle with FES for 1 hour, and cool down of 2 minutes. The ergometer software will be set to provide motor support once muscle fatigue has been reached so the subjects can continue. The subjects will remain seated in their primary wheelchair throughout the treatment. The subjects will cycle for 60 minutes/session, three times a week for 4 months.

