We will be offering FES assisted upper extremity ergometry through our Open Gym program or, if rehabilitative care requires it, though an ongoing, patient tailored program.

b. Devices

1. Name of Test Device:

RT300-SLSA

Manufactured by: Restorative Therapies, Inc
[name]
[name]
[contact]
[contact]

2. Schedule/duration/administration of test device:

The RT300-SLSA Cycle Ergometer is the only device capable of upper extremity cycle ergometry with and without FES, for use in the study.

The device will be used for 1 hour, three times a week, for 4 month,, by both the FES and Control group. For the Treatment group, the device will be programmed to deliver synchronized electrical pulses to the upper extremities. For the Control group, the device will be programmed to drive the cycling of the upper extremities.

Device Risk Assessment: The RT300-SLSA cycle ergometer is a motorized system that allow for purely passive, active, or assisted control over leg or arm cycling. The stimulation system is fully integrated with leg and arm motors (“dynamic motor support”) with unilateral or bilateral stimulation option, allowing for individualized usage for upper and lower extremities. The systems allow for the individual to remain in his/her wheelchair, insuring easy usage across subjects without transfer of the subjects. The speed of cycling can be changed from zero to sixty revolutions per minute (rev/min) and the load (resistance) can be adjusted from zero to 17 Newton-meters (Nm). The system has numerous safety features, such as muscle spasm detection and arm guides, that make it ideal for use in this study. The system have internet connectivity allowing the retrieval of subject settings and the automatic collection of cycling data, ensuring easy use across subjects in this study.

All the ergometers that will be used for this study will be checked and tagged by Johns Hopkins Hospital Clinical Engineering Services (CES). The local IRB of Record does require an approval letter from CES regarding the use of the device in the study. The approval letter is part of the application to the local IRB of Record.

3. FDA Status:

The device is classified as an external functional neuromuscular stimulator (CFR 882.5810). The device is FDA cleared under section 510(k). The device clearance number is K072398.

The device will be used in a research mode that:

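### Baseline adjustment depends on a significant homogeneity test, which can cost power in a month-4 FES versus non-FES comparison; the outcome scale and contrast are not named

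*Combined protocol and SAP*

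**What the plan says.** Section XI.c.3 (Data Analysis) first announces a test: "Baseline tests of homogeneity will be used". It then makes adjustment depend on the result: "If statistically significant differences are found after the subjects are randomized to the two groups, they will be corrected in the post-hoc analysis". It does not name the test, its threshold or the form of the correction. No other baseline adjustment appears in the document.

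The main analysis is given in one sentence: "Appropriate post-hoc statistical analysis will be used to compare between group means and repeated measures". No model, visit or scale (end score or change) is stated. Section XI.c.1 gives the independent variable as FES or no FES, with measurement at months 0, 4, 5, 9 and 12 (no shoulder film at month 5).

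The design is a two-sequence crossover. Section VII.b states: "A 12 months randomized, controlled, single-blinded, in-subject controlled (A-B type) trial will be performed in patients with SCI". Under Intervention (XI.a.1), a group is a treatment order: subjects are assigned "either to group 1, which will first engage in the FES assisted ergometry followed by the non-FES assisted exercise", or to the reverse order. In XI.b.2 a group is a treatment condition, the device being used "by both the FES and Control group". Section IX.b plans 24 randomized as 12 and 12, with at most 4 lost.

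**The concern.** Once subjects are randomized, any baseline difference is due to chance, and a significance test of it answers no useful question. What decides whether adjustment helps is how strongly the month-0 value predicts the later value. The homogeneity test does not measure that.

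A between-group comparison at month 4 could therefore be left unadjusted in about 95% of cases, although every listed outcome is measured at month 0. With only 24 subjects that precision matters. Because each outcome would get its own test, some may be adjusted and others not, for no reason beyond chance.

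How much this costs depends on something the plan leaves open: whether the FES effect is a month-4 difference in end scores, a difference in change, or a within-subject contrast across the two periods. The section on the power analysis gives measuring the magnitude of the effect for future trials as one of the study's goals, and that needs the contrast to be fixed beforehand.

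**Working it through.** The plan gives no figure on this point to reproduce: no effect size, SD, correlation or power is stated.

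**Inputs from the documents:** 12 per group (IX.b, XI.a.1), significance level 0.05 (XI.c.3), outcomes at months 0 and 4.

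**Assumed:** two-sided tests, normal data, equal SDs, baseline test at 0.05, correction meaning ANCOVA on the month-0 value, and month 0-4 correlation ρ of 0.3, 0.5, 0.7 or 0.8.

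**1. When the rule acts.** By chance it acts in 5% of tests. At 12 per group the observed imbalance must exceed t(0.975; 22 df) × √(2/12) = 2.074 × 0.408 = 0.85 SD.

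**2. What adjustment is worth at month 4 (large-sample variances, n per group).** End scores: 2σ²/n. Change scores: 4σ²(1−ρ)/n. ANCOVA: 2σ²(1−ρ²)/n.
- ANCOVA relative to end scores: 1−ρ² = 0.91/0.75/0.51/0.36.
- ANCOVA relative to change scores: (1+ρ)/2 = 0.65/0.75/0.85/0.90.

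**3. Simulated power (%), 12 per group, true difference 0.8 SD, 500,000 trials per setting.** The rule uses unadjusted end scores and switches to ANCOVA if the baseline test is significant.

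| ρ | Rule on end scores | Change scores | Always ANCOVA | ANCOVA minus rule | ANCOVA minus change |
|---|---|---|---|---|---|
| 0.3 | 46.2 | 35.3 | 48.1 | 1.9 | 12.8 |
| 0.5 | 46.6 | 46.7 | 56.0 | 9.4 | 9.3 |
| 0.7 | 47.2 | 67.5 | 72.4 | 25.2 | 4.9 |
| 0.8 | 47.8 | 84.1 | 85.9 | 38.1 | 1.8 |

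An independent repeat agreed within 0.3 points.

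Sensitivity to the assumed effect, at ρ = 0.3/0.5/0.7/0.8:
- Rule on end scores: loss of 1/5/15/26 points at 0.5 SD and 2/8/15/17 at 1.2 SD.
- Change scores: ANCOVA gains 6/5/3/2 points at 0.5 SD and 16/8/2/0 at 1.2 SD.
- With 10 per group and 0.8 SD, the rule on end scores loses 2/8/23/38.

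**4. Type I error of the rule on end scores, 12 per group:** 4.8/4.4/3.7/3.1%.

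**5. Within-subject contrast.** With 10 per sequence, no carryover, equal correlation between visits and an effect of 0.66 SD of the within-subject difference, simulated power is 79.4 to 79.9% without the rule and 78.7 to 79.2% with it.

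**6. What a sequence-group difference estimates.** Let d be the FES-minus-non-FES effect and λ the share of it that persists to month 9. Take the FES-first group minus the other.
- Month 4: +d.
- Month 9: λd − d = −(1−λ)d, which is −d without carryover.
- Month 12: both sequences have had both treatments, so the difference does not estimate d.
- Crossover contrast, half the month-4 minus month-9 difference: [d + (1−λ)d]/2 = d(1−λ/2), that is 1.00d, 0.75d and 0.50d at λ = 0, 0.5 and 1.

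**7. Precision of the two candidate contrasts.** With N subjects in both and the same ρ between all visits, the crossover variance is 2σ²(1−ρ)/N and the month-4 ANCOVA variance is 4σ²(1−ρ²)/N. The ratio is 1/[2(1+ρ)] = 0.38/0.33/0.29/0.28.

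**The case against.** The strongest reply is that the costly case is the one the text supports least. The trial is described as controlled within subjects, the analysis sentence mentions repeated measures, and the power paragraph speaks of pre and post: "A sample size of 24 will allow us to detect a mean difference between the pre- and post-measures". A within-subject contrast loses under 1 point. A change-score or repeated-measures analysis uses month 0 whatever the homogeneity test shows. The ANCOVA gain over change scores also reflects the choice of analysis more than the conditional rule itself.

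Much of this stands. A reader might infer that the baseline data will go unused in most comparisons. The documents do not support that, because they do not commit to end scores. What remains is that the only adjustment written down depends on a significance test, and no named model or scale removes that dependence.

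A reader might also take the opposite signs at months 4 and 9 as a flaw in the design. They are not. The sentence on baseline correction refers to the two randomized groups, which are sequences, and the sign reversal is what the crossover estimator uses. The gap is that the plan does not write the contrast down.

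**Conclusion.** The point holds in a limited form. Making adjustment conditional on a baseline test has no inferential basis, and adjusting always is a free improvement for any month-4 comparison between groups. At 0.8 SD and 12 per group the cost of the rule on end scores ranges from about 2 points (correlation 0.3) to 38 (correlation 0.8). The large losses need both raw end scores and a high correlation. With change scores the shortfall against ANCOVA is about 13 points at correlation 0.3 and 2 at 0.8. All these figures rest on assumed normal data, effect sizes and correlations.

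A reader might infer that the rule produces false positives. Averaged over randomizations it does not: type I error is at or below 5%. The unnamed scale and contrast are mainly missing detail, but they decide which of these costs applies, and a between-group test at month 12 would not estimate the FES effect at all. This should be fixed; it does not invalidate the trial.

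**What to change.** 1. Delete the two sentences on baseline testing in XI.c.3. Baseline values can still be tabulated by sequence.
2. Adjust every month-4 FES versus non-FES comparison for the month-0 value of the same outcome, whatever the observed baseline difference. Use ANCOVA, or a rank-based or ordinal version for the scales that XI.a.1 labels ordinal.
3. State in advance which contrast is the FES effect: the within-subject contrast of months 4 and 9 with treatment and period terms, or the month-4 ANCOVA. Report the other as supportive. Do not choose by a carryover test, which would again let a preliminary test pick the analysis. Report month 12 by sequence, descriptively.

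The choice in step 3 is the sponsor's. The crossover contrast is usually more precise but shrinks toward zero if the FES effect persists past the washout. The month-4 ANCOVA is free of carryover but needs a larger effect. Subluxation can use either, since films are scheduled at months 0, 4 and 9.

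The cost is wording, submitted by the amendment route in XVIII.a, with no new visit or measurement. ANCOVA uses one degree of freedom for the covariate and assumes a roughly linear relation with baseline.
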